1.3 Schedule of Assessments

Table 1Schedule of Assessments

	Screening Period		Treatment Period			Follow up period
Assessments	Visit 1	Visit 2 (Baseline)	Visit 3	Visit 4	Visit 5 (EoT) ⁹	Visit 6 (T/V ¹) or at Discontinuation of the Post treatment (End of Study) ^{11,12}
Week	-1 to -2	0	4	8	12	14
Visit Window (Days)	0	±2	±3	±3	±3	±3
Visit Number	1	2	3	4	5	6
Obtaining Informed Consent	Х					
Inclusion/Exclusion Criteria	Х	Х				
Medical History	Х					
Demographics	Х					
Physical Examination	Х				Х	
Randomization		Х				
Dispense/Collect IP		Х	Х	Х	Х	
Administration of IP ²		Х	←		→	
Issue Bladder e-diary	X ³	Х	Х	Х		
Retrieval of the Bladder e-diary		Х	Х	Х	Х	
OABSS ⁴		Х	Х	Х	Х	
Vital Signs ^{5,9}	Х	Х	Х	Х	Х	
Clinical Laboratory tests ^{6,9}	Х				Х	
Pregnancy Test ⁷	Х				Х	
Routine 12-lead ECG ^{8,9}	Х				Х	
PVR ¹⁰	Х				Х	
Previous and Concomitant Medication	Х	Х	Х	Х	Х	Х
AEs		Х	Х	Х	Х	Х

AE: adverse event; CRF: case report form; ECG: electrocardiogram; eCRF: electronic case report form; e-diary: electronic diary; EoT: end of treatment; IP: investigational product; PVR: post void residual; OAB: overactive bladder; OABSS: OAB Symptom Score.

Footnotes continued on next page

22 Mar 2021 Version 2.0

- 1. T/V = Telephone contact or site visit.
- 2. Daily IP administration will start on day 1 (i.e., the day on visit 2/week 0 [baseline]). For 25 mg mirabegron group, a dose escalation to 50 mg is allowable on visit 3 and visit 4 by investigator's discretion.
- 3. For the screening visit (visit 1/week -1 to -2 [screening]), all subjects will start with the completion of a 3-day bladder e-diary which includes collection of micturition volume over 2 days.
- 4. The OABSS questionnaire will be completed on visit 2/week 0 (baseline), visit 3/week 4, visit 4/week 8 and visit 5/week 12 (EoT).
- 5. Blood pressure, pulse measurements and body temperature will be measured in single measurements. Subject to be in the sitting position (when possible, otherwise supine, but always in the same position for each procedure). Subject should have been calm and without distress for at least 5 minutes. Preferably, the right arm should be used to measure vital signs. Body temperature will be measured with an ear thermometer. These measurements will be used to assess eligibility.
- 6. Hematology, biochemistry and urinalysis (urinalysis dipstick) tests will be performed at visit 1/week -1 to -2 (screening) and visit 5/week 12 (EoT). Refer to Table 8 for the list of clinical laboratory tests.

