5.2 Exclusion Criteria

Subject will be excluded from participation in the study if any of the following apply:

Exclusion at Visit 1/Week -1 to -2 (Screening)

- 1. Subject has stress urinary incontinence as a predominant symptom.
- 2. Subject has an average total daily urine volume > 3000 mL (as recorded in a 3-day voiding diary period).
- 3. Subject has indwelling catheter or practices intermittent self-catheterization.
- 4. Subject has neurogenic detrusor overactivity or indicated pathology other than OAB.
- 5. Subject has monosymptomatic enuresis.
- 6. Subject has PVR volume of ≥ 100 mL or a clinically significant lower urinary tract obstructive disease, except if successfully treated.
- 7. Subject has anatomical anomalies (surgically treated or untreated) that affect lower urinary tract function.
- 8. Subject with hematuria on dipstick test. In the case of hematuria on dipstick test in a female during menstruation, the test can be repeated before randomization (after the end of menstruation).
- 9. Subject has lower urinary tract stones or clinically significant kidney stones requiring treatment.
- 10. Subject has interstitial cystitis.
- 11. Subject has suffered from chronic UTI or has had more than 3 UTIs in the 2 months prior to visit 1/week -1 to -2 (screening).
- 12. Subject has uncontrolled hypertension (sitting systolic blood pressure $[SBP] \ge 180 \text{ mmHg}$ or diastolic blood pressure $[DBP] \ge 110 \text{ mmHg}$).
- 13. Subject has pulse rate ≥ 110 beats per minute (bpm) or < 50 bpm.
- Subject has corrected QT interval by Fredericia (QTcF) > 440 msec on screening ECG or a risk of QT prolongation (e.g., hypokalemia, long QT syndrome [LQTS] or family history of LQTS or exercise-induced syncope).
- 15. Subject's aspartate aminotransferase (AST) or alanine aminotransferase (ALT) is
 ≥ 2 × upper limit of normal (ULN) or total bilirubin (TBL) is ≥ 1.5 × ULN according to
 age and sex (subjects with Gilbert's syndrome are excepted from the bilirubin threshold).
- 16. Subject has moderate or severe renal impairment.
- 17. Subject has a symptomatic (symptoms can include pain, fever, hematuria, new onset foul-smelling urine) UTI. Note: if the UTI is treated successfully (clinical recovery: confirmed by dipstick test and repeated dipstick test after 14 days [both should be negative]), the subject can be rescreened.

- 18. Subject has a history or presence of any malignancy (previous or current diagnosis of bladder or prostate cancer).

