- 32. Subject suffers from a symptomatic (symptoms can include pain, fever, hematuria, new onset foul-smelling urine) UTI. Note: if a symptomatic UTI is present, all visit 2/week 0 (baseline) assessments must be postponed until the UTI is successfully treated (clinical recovery: confirmed by dipstick test and repeated dipstick test after 14 days [both should be negative]). The postponed visit 2/week 0 (baseline) should be within 14 days of the intended visit 2/week 0 (baseline).

- 33. Subject with hematuria on dipstick test. In the case of hematuria on dipstick test in a female during menstruation, the test can be repeated before randomization (after the end of menstruation).
- 34. Subject has uncontrolled hypertension (sitting SBP $\ge 180 \text{ mmHg}$ or DBP $\ge 110 \text{ mmHg}$).
- 35. Any reason, in the opinion of the investigator, that makes the subject unsuitable for study participation.

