5.4.1 Rescreening

Rescreening is allowed only in situations in which a subject underwent the screening procedures and due to logistical circumstances, the allocated time window for these tests has expired and the subject is documented as a screen failure. In order to rescreen, a new ICF must be signed and a new subject screening number assigned. Rescreening is only allowed once for an individual subject.

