#### 6.5.4 Electrocardiograms

The baseline value will be the last non-missing value taken on or prior to first dose of study drug. In the "Schedule of Assessment" table in the protocol (Table 1) this "baseline" assessment will be done at screening (Visit 1).

ECG variables will be summarized using mean, standard deviation, median, minimum, and maximum by treatment group total and visit, including changes from baseline for groups with both a baseline and week 12 measurement. Summary of ECG variables will be presented for each visit [visits 1 and 5], and for EoT values. In addition to the ECG variables mentioned in Section 5.4.5, QTcF (msec) (=QT (msec)/([RR (msec)/1000]1/3) will be summarized. Note: unit for QT and RR reported in CRF is msec.

Normal, not clinically significant abnormal, and clinically significant abnormal results as assessed by investigator for the 12 lead ECG along with shift tables will be presented for changes from baseline to Week 12 including local interpretation categories by the following treatment groups:

- Mirabegron 25 mg (Never Up-Titrated)
- Mirabegron 50 mg (As-Randomized)
- Total Mirabegron.

The QTc interval will be summarized using frequency tables for each treatment visit and time point for values of clinical importance using the range criteria below.

Category	QTc Interval Criteria Value (msec)	
Normal	$\leq$ 450	
Borderline	> 450	
Prolonged	> 480	
Clinically significant	> 500	

Note that these categories are cumulative in that subjects satisfying criterion for more extreme category will also be counted in each applicable less extreme category.

The corrected QT interval (i.e., QTcF) will also be summarized by treatment group and visit showing the frequencies of subjects with the following changes from baseline:

Variable	Change from Baseline
QTc Interval (msec)	< 0
	$\geq 0$ and $< 30$
	$\geq$ 30 and < 60
	$\geq$ 60

ECG data will be provided in listing format by site and subject for the SAF.

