### 6.10 Additional Conventions

#### 6.10.1 Analysis Windows

The study protocol gives the total study schedule and the permissible intervals for these visits expressed as the number of days relative to visit 2/baseline. The total time each subject will be in the study will not exceed 16 weeks with a maximum of a screening period of 2 weeks, a maximum of 12 weeks for the investigational period and a maximum of a follow-up period of 2 weeks.

Analyses will not exclude subject data due to the subject's failure to comply with the visit schedule, see Table 5.

The data summary by visits will be done following the analysis windows specified in Table 5.

For Bladder e-diary data. using the Subject Visit (SV) domain: for each diary record find the date from SV that satisfies the condition (Date from SV-7)  $\leq$  Diary Date  $\leq$  Date from SV. Using the corresponding relative day of that date, assign the analysis visit as specified in Table 5.

Analysis Visits	Target day relative to Baseline (Visit 2, Day 1)	Analysis Window (day)	
Bladder e-diary			
Baseline	Day -1	Day -12 to Day -1	
Week 4	Day 28	Day 7 to Day 42	
Week 8	Day 56	Day 43 to Day 70	
Week 12	Day 84	Day 71 to Day 97	
ЕоТ	Day 84	Day 2 to $\leq$ Last dose of study drug	

 Table 5
 Visit Windows for Efficacy and Safety Parameters

Analysis Visits	Target day relative to Baseline (Visit 2, Day 1)	Analysis Window (day)			
OABSS questionnaire					
Baseline	Day 1	Day -12 to Day 1			
Week 4	Day 28	Day 2 to Day 42			
Week 8	Day 56	Day 43 to Day 70			
Week 12	Day 84	Day 71 to Day 97			
ЕоТ	Day 84	Day 2 to $\leq$ Last dose of study drug			
Vital signs*					
Week -2	Day -14	Day -17 to Day -4			
Week 0/ Baseline	Last value prior to first dose	Day -3 to Day 1 (prior to first dose)			
Week 4	Day 28	Day 2 to Day 42			
Week 8	Day 56	Day 43 to Day 70			
Week 12	Day 84	Day 71 to Day 97			
ЕоТ	Day 84	Day 1 to $\leq$ Last dose of study drug			
ECG, Clinical Laboratory Tests (including Pregnancy Test) and PVR*					
Week -2/ Baseline	Day -14	Day -17 to Day 1 (prior to first dose)			
Week 12	Day 84	Day 2 to Day 97			
ЕоТ	Day 84	Day 1 to $\leq$ Last dose of study drug			

\* if an Early Discontinuation visit occurs within any specified visit window, all data collected during this visit will be assigned to the respective analysis visit.

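### Criterion 32's two 14-day limits conflict when a UTI is present at Visit 2, and the Day -17 bound in SAP Table 5 disagrees with the SAP's own baseline definitions for ECG, laboratory tests and PVR

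*Protocol*

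**What the plan says.** **Postponement.** Protocol 5.2, criterion 32, deals with a symptomatic UTI at Visit 2: "all visit 2/week 0 (baseline) assessments must be postponed until the UTI is successfully treated". Successful treatment means clinical recovery, "confirmed by dipstick test and repeated dipstick test after 14 days [both should be negative". The same note then sets the limit: "The postponed visit 2/week 0 (baseline) should be within 14 days of the intended visit 2/week 0 (baseline". Protocol Sections 5 and 7 rule out eligibility waivers.

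**Rescreening.** Criterion 17, the matching rule at Visit 1, says that after successful treatment "the subject can be rescreened". Section 5.4.1 is narrower: "Rescreening is allowed only in situations in which a subject underwent the screening procedures and due to logistical circumstances", the time window for the tests has expired.

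**Timing of the safety tests.** Footnote 6 to Protocol Table 1 reads: "Hematology, biochemistry and urinalysis (urinalysis dipstick) tests will be performed at visit 1/week -1 to -2 (screening) and visit 5/week 12 (EoT". ECG and PVR are also scheduled before dosing only at Visit 1. Criterion 32 does not ask for any of them to be repeated.

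**Baseline in the SAP.** Table 5 (Section 6.10.1) gives the Week -2/Baseline row for ECG, laboratory tests and PVR the window "Day -17 to Day 1 (prior to first dose", and by-visit summaries follow that table. Section 6.5.4 defines the ECG baseline without a lower limit: "The baseline value will be the last non-missing value taken on or prior to first dose of study drug". Sections 6.5.2 (laboratory) and 6.5.6.1 (PVR) use the same definition. Section 5.4.3 takes the Visit 1 value as baseline for laboratory changes and shifts, and turns to another pre-dose value only if Visit 1 is missing.

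**The concern.** The postponement rule sets a minimum delay and a maximum delay. For the case it describes, the minimum appears to exceed the maximum. A site that follows both figures cannot dose the subject. A site that relaxes either one has no waiver to rely on, and may record an entry-criteria deviation (PD1 in SAP 6.2.2). The rescreening route is no clearer, because the two sections that govern it disagree.

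The SAP problem follows from any delay of Visit 2, whatever its cause. The single pre-dose ECG, laboratory panel and PVR move further back from Day 1 and can pass the Day -17 bound, while the text definitions still accept them. At stake are the baseline rows, changes from baseline and shift tables for these tests. QT prolongation and urinary retention are adverse events of special interest (Protocol 7.3.6), so a valid baseline should not depend on which SAP section the programmer reads.

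**Working it through.** **1. Criterion 32**

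Inputs, all from criterion 32: repeat dipstick 14 days after the first negative one; postponed visit no more than 14 days after the intended date. Let t be the day of the first negative dipstick, with the intended Visit 2 as day 0.

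- Earliest permitted Visit 2 = t + 14.
- Cap: t + 14 ≤ 14, so t ≤ 0.
- UTI present on day 0 and first negative dipstick at t ≥ 1: earliest visit = 1 + 14 = day 15, past the cap.
- Assumed 3, 5 or 7 days to a negative dipstick (the documents give no figure): day 17, 19 or 21.
- If the ±2-day window for Visit 2 in Protocol Table 1 also extended the cap: t + 14 ≤ 16, so t ≤ 2. The text does not say that it does.

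**2. SAP Table 5**

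Inputs: Visit 1 is 7 to 14 days before the intended Visit 2 (Protocol Table 1); window opens at Day -17 (SAP Table 5). Let s be the days from Visit 1 to the intended Visit 2, and D the postponement. Taking the actual Visit 2 as Day 1 with no Day 0, Visit 1 falls on Day -(s + D). It lies inside the window when s + D ≤ 17.

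With no delay (D = 0), Visit 1 falls on Day -7 to Day -14, inside the window. The bound therefore works for an undelayed schedule.

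| s (days) | Largest D inside window, 17 - s | Visit 1 when D = 14 |
|---|---|---|
| 7 | 10 | Day -21 |
| 10 | 7 | Day -24 |
| 14 | 3 | Day -28 |

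At the full 14-day postponement every Visit 1 value lies outside Day -17. Letting s vary by ±2 days (5 to 16) gives Day -19 to Day -30, still all outside. With s = 14, a delay of 4 days already gives Day -18. If a Day 0 were counted, each limit in the middle column would rise by 1 day, and D = 14 would still be outside throughout.

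**3. The SAP definitions side by side**

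| Source | Applies to | Lower day limit |
|---|---|---|
| Table 5 | By-visit summaries of ECG, laboratory, PVR | Day -17 |
| 6.5.2, 6.5.4, 6.5.6.1 | Baseline value: laboratory, ECG, PVR | None |
| 5.4.3 | Laboratory changes and shifts: Visit 1 value | None |

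A Visit 1 value at Day -21 is the baseline under the second and third rows, but has no analysis visit under the first. For laboratory tests the second and third rows also differ from each other: if an unscheduled panel is taken between Visit 1 and first dose, 6.5.2 selects that panel and 5.4.3 selects Visit 1.

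**The case against.** **On criterion 32.** A reader might infer that no subject can ever meet both limits. That is too strong. They can be met if the first negative dipstick falls on or before the intended date, for example when a UTI was found and treated during screening. The cap is also worded as should. One could count the 14 days from the intended visit rather than from the first dipstick, and then a visit on day 14 exactly would comply. The text names no such starting point, however, and a repeated test is naturally timed from the first. The conflict stands for a UTI still present on the intended date.

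**On the SAP.** A reader might infer that a postponed subject loses its baseline and drops out of the change and shift tables. The SAP does not say this. Its text definitions keep the Visit 1 value, and Section 6.10.1 states that data are not excluded because a subject missed the visit schedule. The liver categories in 6.5.2.1 use the highest value during the investigational period and the QTc categories in 6.5.4 use absolute values, so neither needs a baseline. What stands is that Table 5 and the definitions disagree and the SAP does not say which prevails.

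**On the link between the two.** If criterion 32 is followed strictly for a UTI present at Visit 2, nobody is validly postponed and the long delay arises only after a deviation. That is fair. The Table 5 conflict does not need the full 14 days or a UTI, though: criteria 8 and 33 let a haematuria dipstick be repeated after menstruation, which can also delay randomization.

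**On criterion 33.** A reader might also infer that haematuria at Visit 2 cannot be assessed because Protocol Table 1 lists no dipstick there. This is weak. Table 1 schedules an eligibility check at Visit 2 and the criterion itself names the dipstick.

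**On timing.** SAP Appendix 9.1 reports 249 subjects already randomized, so rewording eligibility would change little in this trial. That lowers the practical value of the protocol change. It does not affect the SAP correction.

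**Conclusion.** The point holds as an internal inconsistency in each document. In the protocol, when a UTI is present on the intended Visit 2 date and the first negative dipstick comes at least 1 day later, criterion 32 asks for a visit on day 15 or later and forbids one after day 14. Day 17 to 21 rests on the assumed 3 to 7 days. Criterion 17 and Section 5.4.1 separately contradict each other on rescreening.

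In the SAP, a valid Visit 1 value falls outside Table 5 once Visit 2 is delayed by more than 3 to 10 days, depending on when Visit 1 took place. The effect depends on programming: the by-visit baseline rows could omit the value, and so could the change tables if Table 5 is applied literally. Nothing in the SAP requires that outcome.

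The documents give no frequency of UTI or of postponement, so the number of subjects cannot be calculated; it is probably small. The finding concerns the baselines for ECG, laboratory tests and PVR. The primary analysis and the sample size are not affected.

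**What to change.** **Protocol.** Reconcile the repeat-dipstick interval and the postponement limit in criterion 32 so that both can be met, and state whether the Visit 2 window applies to a postponed visit. Reconcile criterion 17 with Section 5.4.1. Which clinical rule stands is for the sponsor to decide. With randomization complete, the main use of this is to establish how any affected subjects are classed as deviations.

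**SAP.** In Table 5, remove the Day -17 lower bound for ECG, laboratory tests and PVR, so that the row matches the definitions in 6.5.2, 6.5.4 and 6.5.6.1. For laboratory tests, also align 5.4.3 (Visit 1 value) with 6.5.2 (last non-missing value before first dose), because removing the bound alone leaves those two in conflict.

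**Cost.** Some protocol wording, one table entry and one sentence in the SAP, which Section 1 allows to be revised before hard lock. No new data are needed. The drawback is that some baseline values will be older; these can be flagged in the listings.

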5.3 Lifestyle Considerations

Restrictions for foods and drinks are not applicable. On visit days dosing should occur in the clinic and breakfast should be eaten at the clinic within 1 hour before dosing.

Concomitant medications such as α 1-AR antagonists, medication for diabetes insipidus (desmopressin, vasopressin), antidepressants (Selective Serotonin Reuptake Inhibitors [SSRIs] or tricyclic antidepressants), 5 α -reductase inhibitors, capsaicin or resiniferatoxin injections into bladder, botulinum toxin injections to bladder muscles, strong cytochrome P450, family 3, subfamily A (CYP3A) inhibitors, antimuscarinics medications for OAB, and those metabolized by CYP2D6 should be restricted during the study except α 1-AR antagonists, 5 α -reductase inhibitors (5-ARIs) and Phosphodiesterase type 5 inhibitors (PED-Is) use for Benign Prostatic Hyperplasia(BPH)

5.4 Screen Failures

A screen failure is defined as a potential subject who signed the ICF but did not meet one or more criteria required for participation in the study and was not enrolled.

For screen failures, the demographic data, date of signing the ICF, inclusion and exclusion criteria, AEs up to the time of screen failure and reason for screen failure will be collected in the electronic case report form (eCRF).

5.4.1 Rescreening

Rescreening is allowed only in situations in which a subject underwent the screening procedures and due to logistical circumstances, the allocated time window for these tests has expired and the subject is documented as a screen failure. In order to rescreen, a new ICF must be signed and a new subject screening number assigned. Rescreening is only allowed once for an individual subject.

6 INVESTIGATIONAL PRODUCT(S)

6.1 Investigational Product(s) Administered

Table 3Investigational Product(s)

Name	Mirabegron (BETMIGA®)		
Use	Test product		
Dosage Form	Sustained-release tablet		
Physical Description	25 mg: oval, brown, film-coated tablet		
	50 mg: oval, yellow, film-coated tablet		
Unit Dose Strength	25 and 50 mg		
22 Mar 2021	Astellas		
Version 2.0			

Packaging and Labeling Route of Administration Administration	10 tablets per PTP sheet, 1 sheet per carton Oral IMP will be administered orally, once daily in the morning around the same time of day and around time of food intake (i.e., within 1 hour after breakfast). Tablets will be administered with a sip of water (tablet should be taken as a whole and should not be chewed, divided or crushed).
IMP or Non-IMP	IMP
Sourcing	Provided locally by study site
IMP: investigational medicinal product;	PTP: Press Through Package.

6.2 Preparation/Handling/Storage/Accountability

6.2.1 Packaging and Labeling

All IP used in this study will be prepared, packaged and labeled under the responsibility of qualified personnel at Astellas Pharma China, Inc. (ACN) or sponsor's designee in accordance with ACN or sponsor's designee standard operating procedures (SOPs), Good Manufacturing Practice (GMP) guidelines, International Council for Harmonisation of Technical Requirements for Pharmaceuticals for Human Use (ICH) Good Clinical Practice (GCP) guidelines and applicable local laws/regulations.

Refer to the product label and package insert for detailed information regarding packaging and labeling of the IP.

6.2.2 Handling, Storage and Accountability

- The investigator or designee must confirm appropriate temperature conditions have been maintained during transit for all IP received and any discrepancies are reported and resolved before use of the IP.
- Only subjects consented in the study may receive IP and only authorized study site personnel may supply or administer IP. Only IP with appropriate expiry/retest date may be dispensed.
- All IP must be stored in a secure, environmentally controlled and monitored (manual or automated) area in accordance with the labeled storage conditions and access must be limited to the investigator and authorized study site personnel.
- The investigator, institution or the head of the medical institution (where applicable) is responsible for accountability, reconciliation and record maintenance (i.e., receipt, reconciliation and final disposition records).
- After final reconciliation is confirmed, further guidance and instructions on final disposition of used and unused IP will be provided.

The site must return all IP (including unused or returned by subject) to the sponsor or designee at the end of study or upon expiration. If due to institutional policy or local law, unused, expired or returned IP cannot be returned to the sponsor or designee the IP may be destroyed according to local law.

